Brief Summary	This RCT will test a new electronic health record module to improve guideline-compliant care of older adults with diabetes. The module incorporates effective behavioral economics (BE) principles to improve the degree to which care of older adults is compliant with Choosing Wisely (CW) guidelines; this generally involves less aggressive targets for HbA1c, and reductions of medications other than metformin. The implementation of the module is triggered by patient scheduling and medication prescribing in EPIC. The BE principles include suggesting alternatives to medications, requiring justification, setting of appropriate default order sets, and incorporation of anchoring and checklists to guide behavior.
Objectives	Primary objective: to test a customized EHR toolkit that applies BE insights to promote appropriate diabetes care in older adults based on the American Geriatric Society's Choosing Wisely guideline, and to assess the acceptability of the resulting module. Secondary objective: to assess the "usability" of the proposed BE-EHR module in clinical practice.
Methodology	Cluster-randomized controlled trial
Endpoints	Primary endpoint: Choosing Wisely guideline compliance Secondary endpoint: medication prescribing patterns
Study Duration	Eighteen months
Participant Duration	Eighteen months
Population	Patients age 75 or older with diabetes
Study Sites	One single site at NYULH consisting of approximately 70 outpatient practices in primary care, geriatrics, or endocrinology
Number of participants	Approximately 5000
Statistical Analysis	We will begin all analyses with descriptive summary statistics and graphical displays of all variables. Primary analyses will utilize Poisson mixed-effects models for the provider-level CW compliance rate, with treatment group as the primary fixed effect of interest and practice as a random effect to accommodate clustering of providers within practices. We will assess whether negative binomial regression is warranted because of overdispersion. We will also explore non-parametric methods such as quantile regression and other rank-based approaches. Although randomization should obviate the need for any additional adjustment, we will explore whether adjustment for provider-level characteristics, such as demographics, panel size, or insurance mix, is necessary.

Schematic of Study Design

Prior to Enrollment	Identify ~70 NYULH clinics to participate
	\int

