Randomization	Randomize evenly in a 1:1 ratio to receive the standard EPIC instantiation or the standard EPIC instantiation plus the BE-EHR module.
	Ţ
Evaluation	Evaluate Choosing Wisely compliance rate in patients meeting eligibility seen at participating practices

1 Key Roles

PI: [name], Professor of Population Health and Director of Biostatistics NYU School of Medicine [name] [contact] [contact]

Sub-I: [name], Associate Professor of Medicine and Population Health NYU School of Medicine [name] [contact] [contact]

Sub-I: [name], Assistant Professor of Medicine and Population Health NYU School of Medicine [name] [contact] [contact]

Sub-I: [name], Assistant Professor of Population Health NYU School of Medicine [name] [contact] [contact]

Sub-I: [name], Postdoctoral Fellow NYU Langone Health [name] [contact] [contact]

2 Introduction, Background Information and Scientific Rationale

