4.4 Study Endpoints

Outcomes measured at the prescription encounter level include whether the prescription is for a diabetes medication other than metformin, and whether the patient's most recent HbA1c value is within the Choosing Wisely HbA1c range guidelines for his/her age and morbidity category; these will be combined to classify the encounter as CW-compliant or CW-noncompliant. Outcomes measured at the physician level include these two measures, aggregated as a proportion of total prescription encounters within all eligible patients.

5 Study Enrollment and Withdrawal

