5.7.3 Premature Termination or Suspension of Study

This study may be temporarily suspended or prematurely terminated if there is sufficient reasonable cause. Written notification, documenting the reason for study suspension or termination, will be provided by the suspending or terminating party to [name], the NIH/NIA, and regulatory authorities. If the study is prematurely terminated or suspended, the PI will promptly inform the IRB and will provide the reason(s) for the termination or suspension.

Circumstances that may warrant termination or suspension include, but are not limited to:

- Determination of unexpected, significant, or unacceptable risk to participants
- Insufficient compliance to protocol requirements
- Data that are not sufficiently complete and/or evaluable
- Determination of futility

Study activities may resume once concerns about safety, protocol compliance, and data quality are addressed and satisfy the sponsor and/or IRB.

6 Study Schedule

Participants will be included in this study by virtue of meeting eligibility criteria and having a patient encounter during the study period (i.e. the trial) of eighteen months from the date of randomization. There are no study-specific visits. Any patient meeting criteria who has one or more patient encounters during the 18-month study period will be included. Therefore, no study-specific visits are relevant for this study, so there is no schedule of visits.

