6.6 Unscheduled Visit

Not applicable.

7 Study Procedures/Evaluations

There are no study-specific procedures that patients will undergo. They will receive care as usual by their outpatient providers. In order to evaluate Choosing Wisely compliance status, the BE-EHR algorithm will capture information on demographics, diagnoses in the patient's problem list, prescription history, and relevant lab results (i.e. allergies and blood glucose (HbA1c)). The study team members will not collect this information directly; data will be collected in NYULH's EHR system, EPIC, and an EPIC Reporting analyst will extract the relevant parameters from the EHR into a report. The study team members only receive the ultimate determination from the algorithm that the patient is either CW-compliant or CW-noncompliant.

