10.2 Sample Size Determination

Our preliminary data indicate that approximately 30-40% of eligible patients have care that is CWcompliant. We wish to be able to detect an increase in the rate of CW-compliant care of ten percentage points or more. We conservatively estimate an ICC (intra-class correlation coefficient, a measure of the degree of additional correlation among providers within the same practice) of 0.05; with an average of four providers per practice site at 70 sites, this leads to a design effect of 1.15. The sample of 280 providers becomes an effective sample size of 244, providing approximately 87% power to detect a difference of ten percentage points between the study arms.

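### Section 4.4 divides by prescription encounters, a denominator the module can change, so an effect achieved by stopping drugs is diluted towards zero

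*Combined protocol and SAP*

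**What the plan says.** Section 4.4 is the only place that sets out how compliance is scored. The elementary record is a prescription: "Outcomes measured at the prescription encounter level include whether the prescription is for a diabetes medication other than metformin". That is combined with whether the latest HbA1c lies in the patient's target range, and each encounter is labelled compliant or noncompliant. At physician level the measures are "aggregated as a proportion of total prescription encounters within all eligible patients". The section does not define a prescription encounter, gives no rule for combining the two components, and does not say how to score a visit at which a drug is stopped and nothing is prescribed.

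The Brief Summary in the Protocol Summary describes what compliant care means: "this generally involves less aggressive targets for HbA1c, and reductions of medications other than metformin". Section 7.1 adds that one nudge fires when a diabetes refill is generated.

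Other places speak of patients:
- Schematic: "Evaluate Choosing Wisely compliance rate in patients meeting eligibility seen at participating practices".
- Section 6: "Any patient meeting criteria who has one or more patient encounters during the 18-month study period will be included".
- Section 7: the study team receives only the determination that "the patient is either CW-compliant or CW-noncompliant".
- Section 10.1: the hypothesis concerns patients in the clinics that receive the module.
- Section 10.2: "approximately 30-40% of eligible patients have care that is CWcompliant".

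Section 10.3 models a provider-level compliance rate and names neither a denominator nor an offset.

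**The concern.** Under Section 4.4 the denominator is generated after randomisation, by the behaviour the module tries to change. Take a patient on one non-metformin drug whose HbA1c is below range. If the clinician stops the drug, there may be no later prescription to score, so the success removes a noncompliant record and adds no compliant one. A comparable usual-care patient left on the drug adds a noncompliant record at each refill.

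The arms would then be compared on sets of records that differ because of treatment. Randomisation does not protect that comparison, and neither the practice random effect nor the negative binomial option in Section 10.3 deals with it. At stake is the primary endpoint: a real gain achieved by stopping drugs would look smaller than it is.

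**Working it through.** **Inputs from Section 10.2.** Control rate 30-40%; target gain 10 points; 70 practices with four providers each (280 providers); ICC 0.05; stated power about 87%.

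**Assumptions, because the documents give no figures.**
- Every patient has the same number of prescription encounters.
- The whole ten-point gain comes from stopping non-metformin drugs in 10 of every 100 patients, all otherwise noncompliant.
- The stop applies from the start of the count, and a stopped patient is truly compliant.
- q is the share of stopped patients with no remaining counted prescription.
- Tests are two-sided at 5% (no alpha is stated).

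**Step 1: the plan's own figures.** Design effect = 1 + (4 − 1) × 0.05 = 1.15, and 280/1.15 = 243.5, which agrees with the stated 244, or 122 per arm. The 87% does not follow from the stated inputs. A two-proportion test with 122 per arm gives 37.3% power for 30% against 40%, 35.7% for 35% against 45%, and 34.8% for 40% against 50% (49.7%, 48.0% and 47.0% one-sided). Comparing provider-level means gives 87% only with a between-provider SD of 0.10/[√(2/122) × (1.960 + 1.126)] = 0.253 (0.282 one-sided). The plan states no SD.

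**Step 2: dilution.** With p the control rate:

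apparent rate = [p + 0.10(1 − q)] / [1 − 0.10q]

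apparent gain = apparent rate − p

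At p = 35% and q = 1, 100 patients become 90 with counted records, of whom 35 are compliant: 35/90 = 38.9%, against 45/100 = 45% among all patients.

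**Step 3: illustrative power.** Taking the 87% at face value, the standard error is 10/(1.960 + 1.126) = 3.24 points, and power = Φ(gain/3.24 − 1.960).

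| Control rate | q | Apparent rate | Apparent gain (points) | Illustrative power |
|---|---|---|---|---|
| 30% | 0 | 40/100 = 40.0% | 10.0 | 87% |
| 30% | 0.5 | 35/95 = 36.8% | 6.8 | 56% |
| 30% | 1 | 30/90 = 33.3% | 3.3 | 18% |
| 35% | 0 | 45/100 = 45.0% | 10.0 | 87% |
| 35% | 0.5 | 40/95 = 42.1% | 7.1 | 59% |
| 35% | 1 | 35/90 = 38.9% | 3.9 | 22% |
| 40% | 0 | 50/100 = 50.0% | 10.0 | 87% |
| 40% | 0.5 | 45/95 = 47.4% | 7.4 | 62% |
| 40% | 1 | 40/90 = 44.4% | 4.4 | 28% |

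The gains in points do not depend on the 87%. The powers do, and inherit its unstated SD.

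**The case against.** The strongest reply is that the encounter-level unit is not settled. The schematic and Sections 6, 7, 10.1 and 10.2 use patient-level wording, and Section 7 says that the team receives a determination for each patient. If that reading governs, the loss need not occur. This stands, and it makes the finding partly one of conflicting passages. It does not remove the problem, because none of those places says how or when a patient is classified. An analyst looking for the scoring rule will find Section 4.4.

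Second, prescription encounter is undefined. If any prescription counts, or if most stopped patients stay on metformin, few leave the denominator. The module promotes metformin through the preference list, which favours that outcome. This also stands: q = 1 is a bound and not an expected value.

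Third, the illustration is simplified. Encounters before a stop remain in the 18-month count, so the dilution could be larger or smaller than shown. Because 4.4 gives no combining rule, a patient whose HbA1c is still below range just after a stop may not yet be classed as compliant.

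Fourth, the secondary endpoint of prescribing patterns might show fewer non-metformin prescriptions. It might, but that does not repair the primary comparison.

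A reader might infer that successful stops go uncounted altogether. The arithmetic does not support this: removing a noncompliant record still raises the proportion, and in the worst case shown 3.3-4.4 of the 10 points remain.

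**Conclusion.** The concern holds as one of dilution. Followed as written, Section 4.4 uses a denominator that depends on treatment and shrinks an effect achieved by stopping a patient's only counted drug. Under the stated assumptions a true ten-point gain appears as 3.3-4.4 points if all stopped patients leave the denominator, 6.8-7.4 if half do, and 10 if none do. The documents do not say where in that range the trial would fall.

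Two stronger readings are not supported. A reader might conclude that the trial's power falls to about 22%. That figure needs q = 1 and a standard error solved back from an 87% that the documented inputs do not reproduce, so it is illustrative only. A reader might also take the encounter-level endpoint as the protocol's fixed choice; five other places are worded for patients. What the documents do support is that the unit and denominator conflict, and that resolving the conflict in favour of 4.4 would lock in the dilution.

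**What to change.** In Sections 4.4 and 10.3:
- Make the primary denominator all eligible patients with any encounter in the 18-month period, which is the Section 6 population.
- Classify each patient once, at a stated fixed time, from prescription history and the most recent HbA1c.
- Count a patient with no active non-metformin diabetes prescription as meeting the medication component, whether or not a prescription was written, and state how the two components combine.
- Keep the prescription-encounter rate as a secondary measure, with prescription encounter defined.

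Use the same unit in Section 10.2, where "an increase in the rate of CW-compliant care of ten percentage points or more" is the target, and state the provider-level SD and alpha behind the power figure.

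The cost is protocol wording and a change to the Epic report; Section 7 already lists prescription history and HbA1c as captured. There are small downsides. Sections 5.4 and 7 do not name an active medication list, so a stop must be inferred from prescription records, with a rule for when a prescription ceases to be active. Patients never on diabetes drugs enter both arms as meeting the medication component. The Section 6 population also depends on encounters after randomisation, but a patient who has been seen stays in it when a drug is stopped.

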5.1 Inclusion Criteria

- Patient at NYULH primary care or endocrinology practice
- Practices that have patients aged 75 or older
- Practices that have a diagnosis of diabetes in the EHR chart

5.2 Exclusion Criteria

• Under age 75

5.3 Vulnerable Subjects

No vulnerable subjects will be enrolled.

5.4 Strategies for Recruitment and Retention

Eligible patients from the chosen practice sites will be identified electronically within EPIC using an algorithm developed by the study team. This algorithm reviews patient records for diabetes codes in the Problem List. Patients 75 and over with one of the included codes are eligible. The algorithm then identifies their life expectancy category using comorbidity codes and assigns them to one of the three Choosing Wisely categories described in Section 4.2. Patients meeting eligibility will be automatically included, and all data collection will take place passively via the NYULH EHR system, EPIC. An EPIC reporting analyst will extract the relevant parameters from EPIC into a report. No study-specific case report forms will be used; rather, information from the patient's problem list, prescription history, and

CONFIDENTIAL

demographics will be used to compute compliance with CW guidelines. Patients from the selected practice sites will undergo their usual interactions with their providers and no study-specific activities will take place.

5.4.1 Use of DataCore/Epic Information for Recruitment Purposes

Eligible patients will be identified electronically within EPIC using an algorithm developed by the study team.

5.5 Duration of Study Participation

Participants will be followed for 18 months.

5.6 Total Number of Participants and Sites

This is a single site study involving approximately 70 NYULH outpatient clinics serving a total of approximately 5000 participants.

5.7 Participant Withdrawal or Termination

5.7.1 Reasons for Withdrawal or Termination

Not applicable as the subjects are recruited at the clinic level.

5.7.2 Handling of Participant Withdrawals or Termination

Not applicable.

5.7.3 Premature Termination or Suspension of Study

This study may be temporarily suspended or prematurely terminated if there is sufficient reasonable cause. Written notification, documenting the reason for study suspension or termination, will be provided by the suspending or terminating party to [name], the NIH/NIA, and regulatory authorities. If the study is prematurely terminated or suspended, the PI will promptly inform the IRB and will provide the reason(s) for the termination or suspension.

Circumstances that may warrant termination or suspension include, but are not limited to:

- Determination of unexpected, significant, or unacceptable risk to participants
- Insufficient compliance to protocol requirements
- Data that are not sufficiently complete and/or evaluable
- Determination of futility

Study activities may resume once concerns about safety, protocol compliance, and data quality are addressed and satisfy the sponsor and/or IRB.

6 Study Schedule

Participants will be included in this study by virtue of meeting eligibility criteria and having a patient encounter during the study period (i.e. the trial) of eighteen months from the date of randomization. There are no study-specific visits. Any patient meeting criteria who has one or more patient encounters during the 18-month study period will be included. Therefore, no study-specific visits are relevant for this study, so there is no schedule of visits.

6.1 Screening

Not applicable.

6.2 Enrollment/Baseline

Not applicable.

CONFIDENTIAL

6.3 Intermediate Visits

Not applicable.

6.4 Final Study Visit

Not applicable.

6.5 Withdrawal Visit

Not applicable.

6.6 Unscheduled Visit

Not applicable.

7 Study Procedures/Evaluations

There are no study-specific procedures that patients will undergo. They will receive care as usual by their outpatient providers. In order to evaluate Choosing Wisely compliance status, the BE-EHR algorithm will capture information on demographics, diagnoses in the patient's problem list, prescription history, and relevant lab results (i.e. allergies and blood glucose (HbA1c)). The study team members will not collect this information directly; data will be collected in NYULH's EHR system, EPIC, and an EPIC Reporting analyst will extract the relevant parameters from the EHR into a report. The study team members only receive the ultimate determination from the algorithm that the patient is either CW-compliant or CW-noncompliant.

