10.3 Statistical Methods

We will begin all analyses with descriptive summary statistics and graphical displays of all variables. Primary analyses will utilize Poisson mixed-effects models for the provider-level CW compliance rate, with treatment group as the primary fixed effect of interest and practice as a random effect to accommodate clustering of providers within practices. We will assess whether negative binomial regression is warranted because of overdispersion. We will also explore non-parametric methods such as quantile regression and other rank-based approaches. Although randomization should obviate the need for any additional adjustment, we will explore whether adjustment for provider-level characteristics, such as demographics, panel size, or insurance mix, is necessary.

11 Source Documents and Access to Source Data/Documents

Source data is all information, original records of clinical findings, observations, or other activities in a study necessary for the reconstruction and evaluation of the study. Source data are contained in source documents. Examples of these original documents, and data records include: hospital records, clinical and office charts, laboratory notes, memoranda, subjects' diaries or evaluation checklists, pharmacy dispensing records, recorded data from automated instruments, copies or transcriptions certified after verification as being accurate and complete, microfiches, photographic negatives, microfilm or magnetic media, x-rays, subject files, and records kept at the pharmacy, at the laboratories, and at medicotechnical departments involved in the study.

The EPIC electronic health record is the primary data collection instrument for the study. Study-specific case report forms will not be used.

Access to study records will be limited to IRB-approved members of the study team. The investigator will permit study-related monitoring, audits, and inspections by the IRB/EC, the sponsor, government regulatory bodies, and University compliance and quality assurance groups of all study related documents (e.g., source documents, regulatory documents, data collection instruments, study data etc.). The investigator will ensure the capability for inspections of applicable study-related facilities (e.g., pharmacy, diagnostic laboratory, etc.).

12 Ethics/Protection of Human Subjects

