12.2 Institutional Review Board

The protocol for study i19-01464, request for waiver of informed consent, and request for waiver of HIPAA authorization will be submitted to the IRB for review and approval. Approval of the protocol, the waiver of consent, and the waiver of HIPAA authorization must be obtained before any participant is enrolled. Any amendment to the protocol will require review and approval by the IRB before the changes are implemented to the study.

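### Section 7 gives the study team only a composite compliant/noncompliant flag, from which the two component measures in 4.4 and the prescribing endpoint cannot be computed

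*Combined protocol and SAP*

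**What the plan says.** Section 7 (Study Procedures/Evaluations) says that "an EPIC Reporting analyst will extract the relevant parameters from the EHR into a report", and then limits what goes further: "The study team members only receive the ultimate determination from the algorithm that the patient is either CW-compliant or CW-noncompliant".

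Section 4.4 starts from the prescription encounter. It names two items, whether the drug is a diabetes medication other than metformin and whether the latest HbA1c lies in the range for the patient's category, and says that "these will be combined to classify the encounter as CW-compliant or CW-noncompliant". It then reports the items separately: "Outcomes measured at the physician level include these two measures, aggregated as a proportion of total prescription encounters".

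The Protocol Summary lists, after the primary endpoint of guideline compliance, "Secondary endpoint: medication prescribing patterns".

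Section 10.3 sets the analysis: "Primary analyses will utilize Poisson mixed-effects models for the provider-level CW compliance rate". Section 10.2 states its planning rate over patients: "approximately 30-40% of eligible patients have care that is" compliant.

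**The concern.** The Section 7 sentence does not just leave detail out. It sets a limit. It follows directly on the statement that an analyst extracts the parameters, and the word *only* separates what the analyst handles from what the team receives. Taken as a specification for the Epic report, it produces a file that cannot support outcomes the protocol defines elsewhere.

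The Protocol Summary describes compliant care as, in general, looser HbA1c targets and fewer drugs other than metformin. The two measures in 4.4 show which of these changed. With the composite alone, a difference between arms could not be traced to prescribing, to HbA1c, or to both, and the secondary endpoint would have no data.

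The unit is a second problem. Sections 7 and 10.2 speak of patients and 4.4 of encounters, so it is unclear what a provider's rate in 10.3 is counted over.

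**Working it through.** The plan states no figure that this point depends on, so there is nothing to reproduce. The check compares what is supplied with what is required.

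**1. Can the two component measures be recovered from the flag?** For each encounter let N = 1 if the drug is not metformin and H = 1 if HbA1c is in range. The flag is one yes/no value computed from the pair, so four combinations collapse to two and the separate proportions are lost. Section 4.4 does not give the combining rule, so I take two possible rules as assumptions, each for 100 encounters of which 35 are compliant (35% is the middle of the 30-40% in 10.2).

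- *Noncompliant only if N = 1 and H = 0.* The 65 noncompliant encounters are fixed at N = 1, H = 0. The 35 compliant ones may be any of the other three combinations. The non-metformin proportion can then be anything from 65% to 65 + 35 = 100%, and the in-range proportion anything from 0% to 35%.
- *Compliant only if N = 0 and H = 1.* The 35 compliant encounters are fixed. The 65 others may be any of the remaining three. The non-metformin proportion runs from 0% to 65%, and the in-range proportion from 35% to 35 + 65 = 100%.

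Under either rule the flag bounds the component measures but does not determine them. This is so even if a flag is supplied for every encounter.

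**2. Can the prescribing endpoint be recovered?** No. The flag does not identify a drug.

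**3. What does the unit change?** Let p be compliance counted over patients, and r the mean number of encounters per noncompliant patient divided by that per compliant patient. If status is constant within a patient, compliance over encounters is p / (p + r(1 − p)). The documents do not give r; I assume 0.5 to 2, the same in both arms.

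| | r = 0.5 | r = 1 | r = 1.5 | r = 2 |
|---|---|---|---|---|
| p = 0.35 | 0.519 | 0.350 | 0.264 | 0.212 |
| p = 0.45 | 0.621 | 0.450 | 0.353 | 0.290 |
| Gain (points) | 10.2 | 10.0 | 8.9 | 7.8 |

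For example, at r = 2, 0.35 / (0.35 + 2 × 0.65) = 0.212. For 0.30 to 0.40 the gains are 11.0, 10.0, 8.5 and 7.4 points; for 0.40 to 0.50 they are 9.5, 10.0, 9.2 and 8.3. The level moves more than the contrast.

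**4. Is the limit lifted elsewhere?**

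- Section 5.4 says prescription history and demographics are used to compute compliance, not that they reach the team.
- Section 10.3 plans descriptive summaries of all variables and possible adjustment for demographics, panel size and insurance mix. It names no source for them.
- Section 12.3.3 has study team members generating Epic reports, and 12.4 mentions a study database. Neither states the contents.
- Section 13.1 makes study staff responsible for data collection, again without listing items.

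These suggest that a fuller dataset was intended. None withdraws the Section 7 limit.

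**The case against.** The strongest reply is that one loosely worded sentence is being read too literally.

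*The flag need not be issued once per patient.* This stands. Section 7 does not say how often the determination is made, and 7.1 describes repeated evaluation: an advisory for patients as they are seen, an alert with each new HbA1c result in a noncompliant patient, and monthly provider rates. A reader might infer a single flag per patient over 18 months, hence about 18 values per provider (5000/280 = 17.9), and conclude that the encounter-level primary outcome cannot be computed. The documents do not support that. A determination made at each encounter would fit both Section 7 and 4.4.

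*The analyst could supply provider-level proportions.* That would solve the problem, and the peer-comparison emails in 7.1 show provider rates already being produced. But those are rates of the composite. No section says that component proportions are passed on, and the limit as written excludes them.

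*Later extraction would not make the analyses post hoc.* This largely stands. Section 4.4 already defines both component measures and their denominator, so pulling the data late would not make them data-driven. Prescribing patterns are not defined further anywhere, but that gap is separate and was not caused by Section 7.

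*The unit arithmetic does not measure harm done by this sentence.* This also stands. The ratios are assumed, and a patient-versus-encounter mismatch already exists between 10.2 and 4.4. Status can also vary within a patient, because one component belongs to the individual prescription.

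*The primary analysis needs only flags linked to provider and practice.* True, and Section 7 can be read as allowing those codes. It does not help the component measures or the secondary endpoint.

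**Conclusion.** The point holds in a limited form. As written, the data described in Section 7 cannot yield either component measure in 4.4 or the secondary prescribing endpoint. That conclusion rests on the text alone and does not depend on how often the flag is issued.

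For the primary outcome, the finding is an ambiguity of unit. The illustration of 52% to 21% by encounter against 35% by patient, with a ten-point gain becoming 10.2 to 7.8 points, rests on assumed encounter ratios of 0.5 to 2, equal in both arms, and on constant status within a patient. It shows why the unit should be stated. It does not estimate bias in this trial.

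The source data exist in Epic and an analyst already extracts them, so this should be corrected before the report is built. It does not call the randomized design into question.

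**What to change.** Replace the Section 7 sentence. For both arms, the Epic analyst supplies one de-identified row per eligible prescription encounter, with:

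- coded patient, provider and practice;
- a drug-class (non-metformin) indicator;
- an HbA1c-in-range indicator;
- the composite compliance flag.

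State in the same place that the primary compliance rate is per prescription encounter, as in 4.4. The two component measures then follow directly, and the prescribing endpoint can be reported at least as the non-metformin share.

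The cost is one protocol amendment with IRB review and a revised report specification. Section 12.2 says a "request for waiver of HIPAA authorization will be submitted to the IRB", so the waiver wording should be checked against the wider extract. The clinical parameters are already extracted under Sections 5.4 and 7, and de-identified storage is planned in 12.3.3 and 12.4. The team should confirm that both indicators can be produced per encounter in the usual-care arm, which the documents do not state.

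The age of the HbA1c value, a life-expectancy category fixed at baseline and a sensitivity analysis using it are optional. They go beyond this defect and would widen patient-level disclosure under the waiver.
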